5.2. Standard clinical care versus extra for research

Indicate which of the methods are part of standard clinical care and which tests and/or visits are extra for research purposes i.e., not standard clinical care.

The testing and scoring of both mattresses is extra for research purposes, i.e.: not standard clinical care. The monitoring of the patient positioning stability will be applied conform standard clinical care.

5.3. Burden and risks

Please describe the burden and risks associated with participation, e.g. the amount and number of blood samples, biopsies, liquor, hair, urine, nails, saliva etc., the number of site visits, physical examinations or other tests, questionnaires or diaries that have to be filled out, physical and psychological discomfort associated with participation.

If there is no burden and risk because there is no direct involvement from participants needed please describe this.

If a study is carried out with minors or incapacitated subjects, it should also be specified whether the risks are negligible and the burden minimal and why the study is group related (i.e., study can only be done using these patients groups).

There is no additional risk introduced by the treatment on a thicker mattress.

The only additional burden of patients in the trial is the additional question asked to score the comfort of both mattresses prior to CT-acquisition, which is considered to be negligible.

5.4. Medical device(s) / In vitro diagnostic tests

Describe which medical device and/or in vitro diagnostic test is used, what the intended use of the medical device is and whether the medical device/diagnostic test is already available in the participating centers.

Both mattresses are not considered to be a medical device. They are not part of the treatment machine, can be safely omitted and their impact on the dose delivery is negligible.

Note here that this study is similar to the example about randomized studies at the CCMO website (https://english.ccmo.nl/investigators/legal-framework-for-medical-scientific-research/your-research-is-it-subject-to-the-wmo-or-not). This example describes a study on the prevention of decubitus, where subjects are randomized to the use of mattress A or B in their bed. Within the context of the WMO no rule of conduct is imposed in this example, and the use of another mattress is not considered as an infringement of the physical and/or psychological integrity of the subject. The website concludes that such randomized studies are not subject to the WMO, providing that no other procedures or rules of behavior are imposed (for instance taking blood samples). Note that he current study does not even randomize.

6. Incidental findings

	6.1.	Chance of incidental findings Is there a chance of incidental findings? ☐ Yes ☑ No
	6.2.	Procedures If yes, describe who will be notified and how the subjects and other parties will be notified in case of incidental findings from the study that may be in the interest for the participant's health.
		Not applicable.
7.	Stati	stical analysis

7.1 Main study parameters/endpoints

Describe how data will be analyzed

Please describe the main study parameters/endpoints.

The percentage of patients that preferred the thick mattress

7.2 Secondary study parameters/endpoints

Please describe the secondary parameters/endpoints, how the analysis will be done for the outcome parameters.

 Average comfort experienced by patients (score: 0-10) while lying on the thin and thicker mattress.

- Average pain experienced by patients (score: 0-10) while lying on the thin and thicker mattress.
- Patient motion

7.3 Other study parameters

Please describe the other parameters/endpoints.

- Treatment site
- Weight

7.4 Analysis

Please describe how the analysis will be done for the outcome parameters.

- The mattress preference is calculated as the fraction of patients that preferred the thick mattress: number of patients who chose the thick mattress / the total number of patients included. Also the confidence intervals will be investigated.
- The experienced comfort per mattress is calculated as the average of the patients' scores.
 Also the distribution of the scores per group (preference for thin vs thick mattress) and confidence intervals will be investigated
- The experienced pain per mattress is calculated as the average of the patients' pain scores.
 Also the distribution of the scores per group (preference for thin vs thick mattress) and confidence intervals will be investigated
- The motion is defined by the translation (in 3D) measured by the AlignRT® camera system, after exclusion from the breathing motion based on a fast Fourier transform.

8. Ethical considerations

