4.5. Sample size calculation

Specify and justify the number of subjects required for the study, estimated number of subjects, or number of subjects in the period of evaluation.

The estimated number of patients needed for evaluation of mattress preference is 36. This number is calculated for a one-sample proportions z-test with an estimated preference for thick mattress of 70%, with ±15% error margin and a confidence level of 95%. These power calculations were performed by [name], statistician at Erasmus MC.

For some patients the optical surface monitoring system may not be able to accurately detect the body of the patients, for instance due to too much body hair. These patients will be included for the primary objective, but cannot be evaluated for the third secondary objective. To account for these patients, accrual will continue until either 36 patients are included that can be evaluated for all objectives or a maximum number of total patients of 45.

5. Methods

[figure not shown]

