5.1. Research methods

Please describe how you conduct research and which methods are used, e.g., questionnaires, human material collection, extraction of data from medical records, analysis of images, the use of an app/medical device/diagnostic test, clinical tests to be performed, etc. Include information

on frequency, duration, volumes. If a Data Management Plan is available, please upload DMP.

Included patients are asked to test the regular and thick mattress for 1 minute each, right before CT scanning. Directly after testing each mattress, patients are asked to score whether they experienced pain lying on any of the mattress (score 0-10) and asked which mattress they prefer. Next the CT scan will be acquired with the mattress of choice. Note that the choice of mattress does not affect the quality of the treatment.

In line with clinical routine, right before treatment, the positioning of the patient on the treatment couch is assessed using an optical surface scanning system. The system acquires a 3D scan of the surface of the patient to verify the patient position right before treatment. To evaluate the quality of the treatment, the patient potion during treatment is also monitored by the same system. Of the 3D surfaces scans that are acquired over time during treatment, only the 3D motion (3 translation and 3 rotations) will be assessed. In the figure below the 3D surface is indicated in white, with the predefined region of interest in yellow. The average motion is shown as the white curve within the green rectangle. All data is stored as radiotherapy treatment information in the context of the treatment. For the research, however, only the 3D motion will be assessed. Next the motion vector will be post-processed using a fast Fourier transform to filter out the breathing motion.

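### Comfort and pain scores split by preferred mattress tend to favour each group's own mattress, so intervals within those groups do not estimate a mattress effect

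*Combined protocol and SAP*

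**What the plan says.** The primary endpoint (section 7.1) is preference: "The percentage of patients that preferred the thick mattress". Section 7.4 handles the two scores in its second and third bullets, each in two steps.

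- First comes an unsplit summary. For comfort: "The experienced comfort per mattress is calculated as the average of the patients' scores". For pain: "The experienced pain per mattress is calculated as the average of the patients' pain scores".
- Then the same sentence is added to both bullets: "Also the distribution of the scores per group (preference for thin vs thick mattress) and confidence intervals will be investigated".

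Section 5.1 places the pain score and the preference question in one test session before the CT scan: "patients are asked to score whether they experienced pain lying on any of the mattress (score 0-10) and asked which mattress they prefer". Section 5.3 places the comfort scoring before the CT scan as well. Section 7.4 names no test for the split and gives no caution on how to read it. It also does not state a within-patient thick-minus-thin comparison, although secondary objective 2 asks whether patients have less pain on the thick mattress.

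**The concern.** The grouping variable is itself an outcome. A patient who happens to score the thick mattress better, for real or by scoring noise, is more likely to say that they prefer it. Grouping by preference therefore partly sorts patients by the direction of their own score difference. The thick-preferring group then tends to show better scores on thick, and the thin-preferring group better scores on thin, even if the average difference over all patients is zero.

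At stake is the reading of the secondary results. Scores for both mattresses, shown per preference group with confidence intervals, invite a comparison of the mattresses within each group. An interval that excludes zero in the thick-preferring group could be taken as evidence that the thick mattress improves comfort or pain, when the sorting alone can produce it. The primary endpoint is not affected.

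**Working it through.** **Inputs from the plan.** Section 4.5 gives the sample size, "The estimated number of patients needed for evaluation of mattress preference is 36", and its basis, "estimated preference for thick mattress of 70%, with ±15% error margin and a confidence level of 95" percent. It caps accrual at 45.

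**The plan's own figure.** n = 1.96² × p(1 − p) / d² = 3.8416 × 0.70 × 0.30 / 0.15² = 35.85, rounded up to 36. The stated number reproduces.

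**Assumptions (not in the documents).** Let D be a patient's thick-minus-thin comfort difference, with true mean 0 and SD 2 points; SDs of 1.5 and 2.5 were also tried. Let ρ be the correlation between D and the underlying tendency to prefer the thick mattress. Both are taken as normal. For pain the signs reverse.

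**Expected difference within each group, 50:50 split.** Mean of D = ±ρ × SD × √(2/π) = ±ρ × 2 × 0.798. At ρ = 0.7 this is ±0.7 × 2 × 0.798 = ±1.12 points. The true average difference is 0 throughout.

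**Simulation.** Trials of 36 patients with equal mattresses, and a 95% t interval for mean D in each preference group:

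| ρ | Group means (thick-preferring / thin-preferring) | One group's interval favours its own mattress |
|---|---|---|
| 0 | 0 / 0 | 2.5% (nominal) |
| 0.3 | +0.48 / −0.48 | about 16% |
| 0.5 | +0.8 / −0.8 | about 41% |
| 0.7 | +1.1 / −1.1 | about 76% |
| 0.9 | +1.4 / −1.4 | about 99% |

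The last column is the rate for a single group. Both intervals favour their own mattress in the same trial in about 58% of trials at ρ = 0.7, and in 11% at ρ of about 0.45.

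**Sensitivity.**

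- *SD:* values of 1.5 or 2.5 rescale the group means but leave the rates essentially unchanged.
- *More patients:* this does not help. At 45 patients and ρ = 0.7 the single-group rate rises to about 86%.
- *A 70:30 split with no average score difference:* at ρ = 0.7 the means are about +0.7 in the thick-preferring group and −1.6 in the thin-preferring group. The intervals favour the group's own mattress in about 48% and 81% of trials. The thin-preferring group then has about 0.30 × 36 = 10.8, or 11, patients.

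**Comparison.** In the same simulated trials, the interval for mean D in all patients, unsplit, excludes zero in about 5%, as it should.

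**The case against.** Several points on the other side are fair.

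- *The split is a supplement.* The main comfort and pain summaries are unsplit averages and do not carry this bias. A reader might infer that the split is the planned analysis of the scores. The text does not support that: the split is an addition, with no test, hypothesis or decision attached.
- *The intervals may not be by group.* In the first bullet of 7.4 the intervals belong to the overall fraction. Read in parallel, those in bullets 2 and 3 could belong to the averages over all patients. The sentence construction favours the by-group reading but does not settle it.
- *The plan states no within-group contrast.* The simulated interval for D within a group is what a reader would be tempted to form from the display; section 7.4 does not specify it.
- *The pattern is not inevitable.* A reader might infer that each group is bound to favour its own mattress. That holds only if preference follows the score difference almost exactly. At ρ = 0 there is no artefact. The documents give neither ρ nor the SD. For pain, many patients may score both mattresses equally, which would weaken the link.
- *Equal means equal on average.* If patients truly differ in which mattress suits them, a positive mean among those who prefer thick correctly describes those patients. It is still not the effect of the mattress in the study population.
- *The split is not irrelevant.* Secondary objective 1 concerns preference among patients with pain, and pain by preference draws on the same data, conditioned the other way.

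These points limit how strongly the concern can be put and support keeping the display. None makes a by-preference interval an estimate of a mattress effect.

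**Conclusion.** The concern holds as a bias in a supplementary analysis; the main score summaries are not at fault. If intervals are reported within preference groups, they will tend to favour each group's own mattress to the extent that scores track preference. The size runs from modest (about 16% for a single group at correlation 0.3) to near certain (99% at 0.9), given equal mattresses, 36 patients, a 50:50 split and normal differences. Comfort is likely to lie towards the upper end, because the primary objective itself treats preference as the measure of which mattress is more comfortable. Pain is less certain. A change before analysis is worthwhile because it also gives secondary objective 2 an interval that is not conditioned on the outcome.

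**What to change.** Amend bullets 2 and 3 of section 7.4 in two respects.

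1. Show the score distributions by preferred mattress without confidence intervals, and label the display as descriptive and not an estimate of a mattress effect.
2. State that the 95% confidence interval is for the mean within-patient thick-minus-thin difference in all tested patients. For pain, name this as the analysis of secondary objective 2; use the same analysis for the comfort scores.

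This also removes the ambiguity about which quantity the intervals belong to. The cost is about two sentences and no new data, since both mattresses are already scored by each patient. The downside is that the by-preference intervals are lost. No added subgroups by "Treatment site" or weight (section 7.3) are needed.

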- 1. To determine if patients who experience pain while lying on any of the matrasses find the thicker radiotherapy matrass more comfortable than the standard thin matrass.
- 2. To determine if the patient experience less pain while lying on the thick matrass compared to while lying on the thin matrass
- 3. To record patient motion during treatment using the optical surface monitoring which is already used in routine clinical practice

Study type

Please describe the design of the study.

A prospective observational study

Study population

Please describe the study population, e.g., healthy volunteers, xx year old.

Only patients (age ≥ 16) with bone metastasis in thoracic, abdominal and pelvis region who are treated at the one-stop shop for palliative radiotherapy are included in this study. The total number of patients that will be included is 45. See section 4.5 for more details.

Methods

Please describe how you conduct research and which methods are used.

The study will be discussed with the patient by the treating physician during intake, or right after by a radiotherapy technologists (RTT). For patients that sign the informed consent, prior to planning-CT acquisition, patients will be asked to lie on each mattresses for 1 minute. Next patients are asked to score the pain they experienced, on a scale of 0-10 while lying on each mattress. Also patients are asked which mattress they prefer. Next the CT scan is acquired of the patients lying on the mattress of choice. The same mattress will also be used during irradiation. Note that both mattresses have been released for clinical use, and the choice of mattress does not affect the quality of the treatment. Only potentially the experienced comfort.

Right before start of treatment and in line with clinical practice, patients will be positioned on the treatment couch with the aid of the optical surface monitoring system. The optical surface monitoring system makes a 3D scan of the surface of the patient from which it calculates the motion (3 translations, 3 rotations) of a predefined region of interest. During treatment, the quality of the treatment is evaluated based on the motion information, and if necessary, RTTs could pause the delivery. Specifically for the study, the motion of the patient will be assessed in more detail after treatment.

Burden and risks

Please describe the burden and risks associated with participation.

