- 2. To determine if the patient experience less pain while lying on the thick matrass compared to while lying on the thin matrass
- 3. To record patient motion during treatment using the optical surface monitoring device that is used in routine clinical practice for patient positioning.

3. Study type

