4.4. Exclusion criteria

A potential subject who meets any of the following criteria will be excluded from participation in this study:

Patients not willing or able to test two mattresses (regular and thicker)

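### Free improvement: state a paired thick-minus-thin interval for pain, because the planned per-mattress averages leave secondary objective 2 without a stated uncertainty

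*Combined protocol and SAP*

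**What the plan says.** The second secondary objective, in the Summary and again in section 2, is a comparison: "To determine if the patient experience less pain while lying on the thick matrass compared to while lying on the thin matrass".

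The design makes it a comparison within patients. Section 5.1 has each patient try both mattresses for one minute each, and section 4.4 excludes "Patients not willing or able to test two mattresses (regular and thicker"). The Summary's Methods paragraph states the measurement: "Next patients are asked to score the pain they experienced, on a scale of 0-10 while lying on each mattress".

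The endpoint in section 7.2 is "Average pain experienced by patients (score: 0-10) while lying on the thin and thicker mattress". Section 7.4 repeats it as a summary for each mattress: "The experienced pain per mattress is calculated as the average of the" patients' pain scores. It then adds the distribution of scores in those who preferred the thin and those who preferred the thick mattress, and confidence intervals, without saying of what quantity. Neither section names a within-patient difference or an interval for one.

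**The concern.** The objective is about a difference, while the planned outputs describe each mattress separately. The split by preference does not bridge the two, because it compares patients according to the mattress they chose, not thick with thin in the same patient.

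If the intervals are calculated for each mattress, which is the nearest reading of 7.4, the report will contain two means and two intervals. A reader can subtract the means but cannot tell how precise the result is. Judging by the overlap of the two intervals would not help, since overlap ignores how closely a patient's two scores move together. Objective 2 would then have a point estimate and no stated uncertainty, and the choice of interval would be made after the data are seen.

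**Working it through.** **The plan's own figure.** Section 4.5 gives 36 patients for a preference of 70%, a margin of ±15% and 95% confidence. Check: n = 1.96² × 0.70 × 0.30 / 0.15² = 35.85, rounded up to 36. The figure reproduces. It concerns the precision of the preference proportion only. The documents give no precision, SD, correlation or effect size for pain.

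**Why per-mattress intervals do not determine the interval for the difference.** With n patients who have both scores:

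- Half-width for one mattress: h = t(n−1) × SD / √n.
- SD of the thick-minus-thin difference, equal SDs assumed: SD × √(2(1−ρ)), where ρ is the within-patient correlation.
- Half-width for the mean difference: t(n−1) × SD × √(2(1−ρ)) / √n = h × √(2(1−ρ)).

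The t quantile, n and SD cancel from the ratio, so only ρ has to be assumed:

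| Assumed ρ | √(2(1−ρ)) | Half-width of the difference |
|---|---|---|
| 0 | √2.0 | 1.41h |
| 0.3 | √1.4 | 1.18h |
| 0.5 | √1.0 | 1.00h |
| 0.7 | √0.6 | 0.77h |

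The same pair of per-mattress intervals is therefore compatible with intervals for the difference whose widths vary by 1.414/0.775 = 1.8-fold over this range. The ratio depends on the range chosen: 1.183/0.775 = 1.5-fold over 0.3 to 0.7, and 1.414/0.447 = 3.2-fold over 0 to 0.9.

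**Illustration in score points.** This assumes n = 36 and SD 2.5 on both mattresses, so h = 0.85. The half-width of the difference is then 1.20, 1.00, 0.85 and 0.66 at ρ = 0, 0.3, 0.5 and 0.7. For SDs of 2 to 3 it runs from 0.96 to 1.44 at ρ = 0 and from 0.52 to 0.79 at ρ = 0.7. Suppose the observed difference were 1 point. With SD 2.5, the interval would extend from 1 − 1.20 = −0.20 to 1 + 1.20 = 2.20 at ρ = 0, and from 1 − 0.66 = 0.34 to 1 + 0.66 = 1.66 at ρ = 0.7. The first includes zero and the second does not, although the per-mattress means and intervals are identical.

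**The case against.** The strongest reply is that 7.4 plans confidence intervals without naming their target, so an interval for the difference is not excluded. If paired scores are collected, it can also be calculated at analysis. This is a secondary endpoint with no sample-size claim, in a single-centre observational evaluation. All of that is fair. It limits the point to an unstated target and an unfixed method, and shows that nothing is lost beyond recovery. It does not remove the gap, because the objective is worded as a question to be settled and the stated summaries do not settle it. The magnitudes above are general algebra with assumed correlations, not estimates for this population.

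A reader might also infer more than the documents support:

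- **That the plan treats the two sets of scores as independent.** No unpaired test or interval is proposed, so the width or power lost by ignoring the pairing is not a loss under this plan.
- **That only one pain score is recorded.** Section 5.1 has patients "score whether they experienced pain lying on any of the mattress (score 0-10"), which is loose if read alone. The same sentence places the scoring straight after each mattress is tried, and the Summary, 7.2 and 7.4 all describe pain for each mattress. This is an editorial matter.
- **That comfort is analysed but never collected.** Section 5.1 does not mention a comfort score, but section 5.3 describes "the additional question asked to score the comfort of both mattresses prior to CT-acquisition", and 7.2 gives its scale: "Average comfort experienced by patients (score: 0-10) while lying on the thin and thicker mattress". This too is editorial. The questionnaire is listed as an attachment but is not among the documents reviewed, so nothing can be said against it.

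**Conclusion.** The point holds as a free improvement. Sections 7.2 and 7.4 give objective 2 a valid point estimate, provided both scores are present, but no stated interval for the comparison, and per-mattress intervals cannot stand in for one. The half-width of the difference is between 1.41h and 0.77h for assumed correlations from 0 to 0.7, with equal SDs assumed. That the interval is not stated follows from the text alone. The size rests on those assumptions, since the documents give no data on pain scores. It would be wrong to conclude that the planned averages are incorrect, or that the study's main result is at risk: the preference endpoint and the 36 patients stand as they are. The gain is a correctly targeted, pre-stated measure of uncertainty for one secondary objective.

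**What to change.** In 7.2 and 7.4, define the pain endpoint for objective 2 as each patient's thick-minus-thin score. Report the mean difference with a two-sided 95% paired confidence interval (mean difference ± t(n−1) × SD of the differences / √n) and the number of patients with both scores. Keep the per-mattress means and the distributions by preference group as description. The same paired summary may be used for the comfort scores.

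Two editorial changes can be made at the same time: say in 5.1 that one pain score is recorded for each mattress, as the Summary does, and mention the comfort score there.

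The cost is a few sentences. No patients, visits or measurements are added if the scores are collected as the Summary, 5.3 and 7.2 describe. The sponsor can confirm from the questionnaire that it records both scores for each mattress. The wording should be settled before the scores are analysed.
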